be switched to oral fluconazole at a dose of 6 mg/kilogram (kg) (rounded to the nearest 200 mg increment) with a maximum dose of 800 mg (e.g., a subject weighing 73 kg would receive fluconazole 400 mg dose [2 capsules of 200 mg each] based on a 6 mg/kg target dose of 438 mg based on weight [$73 \text{ kg} \times 6 \text{ mg/kg} = 438 \text{ mg}$]). NOTE: Refer to dosing section of protocol for alternative regimens of fluconazole in subjects with renal impairment). To maintain the blind, subjects in the caspofungin treatment group who have switched to oral step-down therapy will receive placebo for Rezafungin for Injection IV once weekly on the days of scheduled Rezafungin for Injection doses until study drug is stopped (on Day 8, Day 15 and Day 22 [if applicable]).

Subjects will complete an End of Treatment visit within 2 calendar days after the last dose of study drug and a Follow-up visit within the Day 52-59 period. Subjects who stop study drug prior to Day 22 and are considered clinical failures (i.e., require a change in antifungal therapy to treat candidemia and/or invasive candidiasis) may have their Follow-up visit earlier but the visit must still be ≥ 30 days following the last once weekly infusion of Rezafungin for Injection/placebo.

The study design diagram is provided in [Appendix 1 \(Section 5.1\)](#). The schedule of Assessments and procedures for the required treatment, End of Treatment, and Follow-up periods can be found in [Appendix 2 \(Section 5.2\)](#). The schedule of assessments and procedures for the optional treatment period dosing schedule is shown in [Appendix 3 \(Section 5.3\)](#). The dosing schedule by day can be found in [Appendix 4 \(Section 5.4\)](#).

Alternative caspofungin regimens and guidance for special populations (moderate hepatic impairment; subjects weighing >80 kg or on concomitant rifampin, nevirapine, efavirenz, phenytoin, dexamethasone, or carbamazepine; use of concomitant cyclosporine; or renal impairment) can be found in the protocol.

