2.2.2. Mycological response

Mycological response will be programmatically determined from the electronic case report form (eCRF) and central mycology data (or local mycology data if central is not available) at Day 5, Day 14 (±1 day), Day 30 (-2 days), End of Treatment, and Follow-up (Days 52-59), according to the definitions in Table 2-3.

Table 2-3: Mycological Response Definitions**

Mycological Response	Definition
Eradication*	
 • If positive blood culture at baseline: 
 ○ The last blood culture drawn following the first dose of study drug on or prior to the day of assessments is negative • If positive culture from a normally sterile site at baseline (other than blood): 
 ○ Documented mycological eradication: most recent culture on or prior to the day of assessment from all normally sterile sites of baseline Candida infection (if accessible) is negative and culture was obtained after the initiation of study drug 
OR
 
 ○ Presumed mycological eradication: follow-up culture from all normally sterile sites of baseline Candida infection is not available (eg, normally sterile baseline site of Candida infection not accessible) or the most recent culture from all normally sterile sites of baseline Candida infection obtained after the initiation of study drug is positive, in a subject with a successful clinical outcome as assessed by the Investigator (ie, did not receive rescue antifungal treatment and has resolution of systemic signs and symptoms of invasive candidiasis that were present at baseline) and the subject has a successful radiological outcome (for those with documented evidence of disease from imaging at baseline), 
AND
 
 • There was no change of antifungal therapy for the treatment of candidemia and/or invasive candidiasis, 
AND
 
 • The subject is not lost to follow up on the day of assessment.

Mycological Response	Definition

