Failure	
 • If positive blood culture at baseline: 
 ○ The last blood culture drawn on or prior to the day of assessment is positive for Candida spp from a sample drawn following the first dose of study drug, OR • If positive culture from a normally sterile site at baseline: 
 ○ Documented mycological persistence: culture on the day of assessment from all normally sterile sites of baseline Candida infection (if accessible) is positive, OR ○ Presumed mycological persistence: follow-up culture from all normally sterile sites of baseline Candida infection is not available (eg, normally sterile baseline site of Candida infection not accessible) OR the most recent culture from all normally sterile sites of baseline Candida infection obtained after initiation of study drug is positive, in a subject without a successful clinical outcome as assessed by the Investigator or without a successful radiological outcome for those with documented evidence of disease from imaging at baseline, OR • The subject requires a change of antifungal therapy to treat candidemia and/or invasive candidiasis***, OR • The subject dies of any cause prior to or on the day of assessment.
Indeterminate	
Study data are not available for the evaluation of efficacy for any reason including:
 
 • If positive blood culture at baseline: A post-baseline blood specimen was not available to culture or the result was not available. • If positive culture from a normally sterile site at baseline: A sterile site/fluid post-baseline specimen was not available to culture or the result was not available AND an assessment clinical response by the Investigator was not available or radiographic assessments are not available. • Subject is lost to follow-up on the day of assessment.

* Presumed eradication is defined only for a culture from a normally sterile site and is not defined for a blood culture.

**Table includes clarifications that are not in the protocol.

*** Defined as receipt of an antifungal with an indication of Candidemia/invasive candidiasis, *Candida* endophthalmitis/chorioretinitis or *Candida* endocarditis which started on or prior to the day of assessment or started on EOT (+ 1 day).

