Cure	
 • Resolution of attributable systemic signs and symptoms of candidemia and/or invasive candidiasis that were present at baseline, AND • No new systemic signs or symptoms attributable to candidemia and/or invasive candidiasis, AND • No new systemic antifungal therapy to treat candidemia and/or invasive candidiasis, AND • The subject is alive.
Failure	
 • Progression or recurrence of attributable systemic signs or symptoms of candidemia and/or invasive candidiasis, OR • Lack of resolution of attributable systemic signs or symptoms of candidemia and/or invasive candidiasis, OR • Requirement for new systemic antifungal or prolonged therapy to treat candidemia and/or invasive candidiasis *, OR • An AE requires discontinuation of study drug therapy (IV and IV/oral) on or prior to the day of assessment, OR • The subject died of any cause.
Indeterminate	
 • Study data are not available for the evaluation of efficacy for any reason including: 
 ○ Lost to follow-up, ○ Withdrawal of consent, ○ Extenuating circumstances that preclude the classification of clinical outcome of candidemia and/or invasive candidiasis, ○ Assessment not done.

AE = adverse event; IV = intravenous.

* Prolonged antifungal therapy is defined as therapy for the treatment of candidemia and/or invasive candidiasis extending beyond the allowable 28 days of study drug. The determination of prolonged therapy will only apply to the Follow-up visit clinical response assessment.

The clinical cure as assessed by the Investigator rate is the proportion of subjects with a cure out of the total number of subjects in the specified analysis population.

If a subject discontinued the study medication prior to Day 14 and the Investigator assessed response at the EOT visit is failure, the response at Day 14 for that subject is failure. If study drug was stopped early because the Investigator thought the subject was a clinical cure, the subject must be assessed during the Day 14 window. If the subject did not have the assessment, the response for that subject at Day 14 is indeterminate.

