5. APPENDICES

5.1. Appendix 1: Study Design Diagram

- (a) After ≥ 3 days of IV study drug (or the minimum duration of IV therapy advised by the site's national/regional/local guidelines, whichever is greater), subjects are permitted to switch to oral step-down therapy so long as all criteria is met as specified in the protocol. Subjects who are switched to oral step-down therapy may switch back to IV study drug therapy in the event of the development of a condition that prevents the subject from taking oral medications (e.g., pancreatitis, urgent surgery), but may not switch back to IV study drug therapy for relapse of candidemia/IC or for intolerance or toxicity due to study drug.
- (b) Day 14 is the last required dose of study drug and Day 28 is the last possible dose of study drug. An End of Treatment visit is required ≤ 2 calendar days after last dose of study drug.
- (c) Follow-up will occur between Days 52–59. Subjects who stop study drug early (i.e. clinical failure) and require a change in antifungal therapy to treat candidemia and/or invasive candidiasis may have an earlier Follow-up visit occurring ≥ 30 days from the last weekly dose of IV rezafungin or IV placebo.
- (d) Subjects will complete an End of Treatment visit ≤ 2 calendar days after the last dose of study drug. All safety assessments are to be completed at the End of Treatment visit. Efficacy assessments are also to be completed at the End of Treatment visit.

5.2. Appendix 2: Schedule of Assessments and Procedures for the Required Treatment, End of Treatment, and Follow-up Periods

Assessment or Procedure	Screening ≤4 days (96 hours) before randomization	Required Treatment Period (Days)								Day 30 (-2) Efficacy, Safety	EOT ≤2 days after last dose (IV or oral)	Follow-up ^c Days 52–59
		1 ^a	2	3	4	5–7	8 (±1) ^b	9–13	14 (±1) ^b			
Informed consent ^d	X											
Medical history ^e	X											
Physical examination, including weight and height ^f	X	X ^g	X ^g	X ^g	X ^g	X ^h	X ^g	X ^g	X	X	X	X
Neurological examination ^h	X	X ^h	X ^h	X ^h	X ^h	X ^h	X ^h	X ^h	X ^h	X ^h	X	X ^h
Vital signs ⁱ	X	X	X	X	X	X	X	X	X	X	X	X
Assess Central Venous Catheters ^j	X	X	X	X	X	X	X	X	X	X	X	
Blood for hematology and chemistry tests (see Appendix 3 of Protocol)	X	X	X		X		X		X	X	X	X
Blood for PT/INR (see Appendix 3 of Protocol)	X											

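### The change-of-therapy footnote in SAP Table 2-3 has no time limit on its EOT limb, so a switch of antifungal at EOT after Day 14 also makes the subject a mycological failure at Day 5 and Day 14

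*SAP*

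**What the plan says.** SAP 2.2.2 states: "Mycological response will be programmatically determined from the electronic case report form (eCRF) and central mycology data" (local data if central are missing). The definitions in Table 2-3 are applied "at Day 5, Day 14 (±1 day), Day 30 (-2 days), End of Treatment, and Follow-up (Days 52-59").

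In the failure row, one criterion that suffices on its own is "The subject requires a change of antifungal therapy to treat candidemia and/or invasive candidiasis". A footnote defines it as receipt of an antifungal for candidemia/invasive candidiasis, Candida endophthalmitis/chorioretinitis or Candida endocarditis, "which started on or prior to the day of assessment or started on EOT (+ 1 day"). A note to the table says that it contains clarifications absent from the protocol. The EOT limb is one of them: the matching criterion in protocol Table 8 has no EOT limb and no date at all.

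On timing, SAP Appendix 1 says "Day 28 is the last possible dose of study drug", and SAP 1.2 says "Subjects will complete an End of Treatment visit within 2 calendar days after the last dose of study drug".

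**The concern.** Mycological response at a visit should describe the subject's state up to that visit. The first limb of the footnote does this, because the drug must have begun by the assessment day. The second limb does not mention the assessment day. It is not confined to the EOT visit, nor to visits on or after EOT. No other text in either document narrows it, and a program will follow the words.

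The setting is foreseeable. Study drug stops by Day 28, and protocol 7.4.2 contemplates further antifungal therapy after study drug for some forms of invasive candidiasis. The day of the last dose, or the day after, is a natural start date.

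At stake are the secondary eradication rates at Day 5 and Day 14 (SAP 2.2 and 4.3.2) and the Day 14 summaries by baseline species and MIC (SAP 2.3.4), where cells are small and one subject counts for more. These would depend on events up to two weeks or more after the visit.

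**Working it through.** The plan states no figure to reproduce here. The check is of the rule's logic.

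**Inputs.** *s* = start day of the listed-indication antifungal; *E* = EOT date; *a* = day of the assessment being scored. Visits are Day 5, Day 14, Day 30, EOT and Follow-up (Day 55 used, within Days 52-59).

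**Rule as written.** Failure at *a* if *s* ≤ *a*, or if *E* ≤ *s* ≤ *E* + 1. The first limb already takes every start up to the assessment. The second can therefore add only starts after it, with no limit on how long after.

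**Bounded rule.** Failure at *a* if *s* ≤ *a*, or if *E* ≤ *a* and *E* ≤ *s* ≤ *E* + 1. In whole days the second limb now adds one case only: EOT falls on the assessment day and the switch is the next day (*E* = *a*, *s* = *a* + 1).

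**Results** (F = failure on this criterion, – = not):

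| EOT date | Start | Rule | Day 5 | Day 14 | Day 30 | EOT | Follow-up |
|---|---|---|---|---|---|---|---|
| 28 | 28 or 29 | as written | F | F | F | F | F |
| 28 | 28 or 29 | bounded | – | – | F | F | F |
| 28 | 30 | both | – | – | F | – | F |
| 21 | 21 or 22 | as written | F | F | F | F | F |
| 21 | 21 or 22 | bounded | – | – | F | F | F |
| 15 | 15 or 16 | as written | F | F | F | F | F |
| 15 | 15 or 16 | bounded | – | – | F | F | F |
| 14 | 15 | as written | F | F | F | F | F |
| 14 | 15 | bounded | – | F | F | F | F |

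With EOT on Day 28, moving the start from Day 29 to Day 30 turns the Day 5 and Day 14 results from failure to no failure on this criterion. Nothing about the subject at Day 5 or Day 14 has changed.

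**Neighbouring rules:**

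- Table 2-3, death: counts only up to and including the assessment day.
- Table 2-3, blood cultures: the last one up to the assessment day decides.
- SAP 2.2.3, rescue therapy for clinical response: received before a time point, it counts there and at later time points, never earlier ones.
- SAP 2.2.1 and 2.2.3, failure carried from EOT to Day 14: only for subjects who stopped study drug before Day 14.

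The EOT limb alone reaches back.

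**Size.** The planned mITT population is 184, or 92 per arm. One affected subject who would otherwise be an eradication lowers that arm's rate by 1/92 = 1.09 points. For illustration only, 3 such subjects in one arm give 3/92 = 3.3 points and 5 give 5/92 = 5.4 points. With *k*₁ and *k*₂ affected, the treatment difference moves by (*k*₂ − *k*₁)/92, so equal numbers cancel.

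**The case against.** The best reply is that the authors meant something narrower. EOT is itself one of the five assessments, the rest of the table works relative to the visit, and the limb was probably added to catch a switch made at or just after EOT. That is likely. It does not settle the matter, because the SAP does not say so and the response is derived by program.

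The limb also has a legitimate job. Under protocol 7.4.2, Day 14 efficacy assessments after premature discontinuation are done at EOT unless the subject is believed cured. Protocol 9.2.10 lets the EOT visit coincide with Day 14. The SAP carries EOT failure to Day 14 for global and clinical response but states no such rule for mycological response. Confining the limb to the EOT assessment alone would therefore misfire: with both assessments on Day 14 and a switch on Day 15, one visit would yield failure at EOT and possibly eradication at Day 14. This objection stands and shapes the fix.

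A reader might infer that the clinical-response table takes the opposite position, because its footnote says "The determination of prolonged therapy will only apply to the Follow-up visit clinical response assessment". That concerns therapy beyond 28 days. The same criterion also lists new systemic antifungal therapy, which is not limited to Follow-up. The sound contrast is the forward-only rescue rule.

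A reader might also infer that the EMA primary endpoint is affected, since Table 2-2 turns mycological failure into global failure. The documents do not establish this. The analysis uses the Data Review Committee's determination, and its charter is not among them.

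**Conclusion.** The point holds as a defect in the wording of a programmed rule. Read as written, any switch to a listed-indication antifungal on EOT or the following day, with EOT after Day 14, is scored as mycological failure at Day 5 and Day 14 whatever the cultures showed then.

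Its reach is limited. Mycological eradication is secondary, and SAP 4.3.2 calls its intervals descriptive. All-cause mortality does not use the rule. The size is 1.1 points per affected subject in an arm, assuming 92 per arm and a subject otherwise classed as eradicated. A total effect of several points might be inferred, but that needs a frequency of switching at EOT, which the documents do not give. Nor do they give any reason to expect more switching in one arm, so bias in the treatment difference is not shown.

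The Day 28-29 example takes the EOT date as Day 28. The footnote does not say whether EOT is the last-dose date or the visit date. After a Day 28 dose the visit may fall as late as Day 30, which moves the window to Days 29-30 or 30-31.

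**What to change.** Reword the footnote along these lines: the antifungal began no later than the day of the assessment; in addition, for the EOT assessment and for any assessment dated on or after the EOT date (including a Day 14 assessment carried out at EOT), it began on the EOT date or the day after.

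State whether EOT means the last-dose date or the EOT visit date. Attach the same definition to the eradication row, whose no-change condition carries neither the footnote mark nor a date.

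The cost is one SAP footnote and the matching line of the derivation program. No data collection, sample size or primary analysis changes.

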2.2.4. Radiological Response

Radiological response is defined in **Table 2-5**. Only subjects with invasive candidiasis, with radiologic or other imaging studies at baseline that demonstrate evidence of invasive candidiasis, should be assessed for this outcome. The radiologic response as assessed by investigator will be summarized.

Table 2-5: Radiological Response Definitions

Radiological Response	Definition ^a
Cure	
 • Improvement or resolution of radiological or other imaging findings of invasive candidiasis that were present at baseline (i.e., the radiograph/imaging study that documented evidence of the invasive candidiasis) 
AND
 
 • No new radiological or other imaging findings attributable to invasive candidiasis, 
AND
 
 • The subject is alive.
Failure	
 • Progression of or new radiological or other imaging findings of invasive candidiasis, 
OR
 
 • Lack of improvement of radiological or other imaging findings of invasive candidiasis, 
OR
 
 • The subject died of any cause.
Indeterminate	
 • Radiological or imaging data are not available for the evaluation of efficacy for any reason including: 
 ○ Lost to follow-up, ○ Withdrawal of consent, ○ Radiology/Imaging not completed ○ Extenuating circumstances that preclude the classification of a radiological outcome of invasive candidiasis

^a Includes radiological or other imaging studies. Only for invasive candidiasis subjects with imaging performed at baseline who had radiological or other imaging studies that documents evidence of invasive candidiasis.

The radiological cure rate as assessed by the Investigator is the proportion of subjects with a cure out of the total number of subjects with invasive candidiasis documented by radiologic/imaging evidence at baseline in the specified analysis population.

2.3. Exploratory Efficacy Outcomes

2.3.1. Resolution of Attributable Systemic Signs of Candidemia and/or Invasive Candidiasis that were Present at Baseline

It is a requirement that at least 1 systemic sign attributable to candidemia and/or IC be present at Screening for the subject to be eligible for enrollment. The Screening period for assessing systemic signs for inclusion in the study may include the 12 hours prior to the drawing of the qualifying positive culture (when systemic signs of infection resulted in obtaining blood cultures), qualifying positive culture from a sterile site, or qualifying rapid in vitro diagnostic, through enrollment. The possible signs of infection that might be attributable to candidemia and/or IC at baseline include fever, hypothermia, hypotension, tachycardia, tachypnea, and local signs of inflammation.

For the listed systemic signs of candidemia, the qualifying parameters are listed below:

Fever: Oral or axillary temperature $\geq 38^{\circ}\text{C}$ [100.4°F] or a tympanic, temporal, rectal, or core body temperature $\geq 38.3^{\circ}\text{C}$ [101°F]

Hypothermia: Tympanic, temporal, rectal, or core body temperature $\leq 35^{\circ}\text{C}$ [95.2°F]

Hypotension: Systolic blood pressure < 90 mmHg or mean arterial pressure < 70 mmHg with a normovolemic or hypervolemic status

Tachycardia: Heart rate > 100 beats per minute with a normovolemic or hypervolemic status

Tachypnea: Respiratory rate > 20 breaths per minute

Local signs of inflammation: Erythema, edema, heat and pain at the site of the qualifying culture

Resolutions of systemic signs will be programmatically categorized as follows:

- Yes (resolution): Resolution of all attributable systemic signs of candidemia and/or invasive candidiasis that were present at baseline and no new attributable systemic signs that were not present at baseline
- No (not resolved): New attributable systemic signs that were not present at baseline or lack of resolution of any attributable systemic signs of candidemia and/or invasive candidiasis that were present at baseline

Subjects whose assessment of systemic signs was not completed at a visit or at baseline for any reason (including death) will not be included in the analysis.

Resolution of systemic signs attributable to candidemia and/or invasive candidiasis for subjects receiving Rezafungin for Injection and caspofungin will be assessed at Day 5, Day 14 (± 1 day), Day 30 (-2 days) and Follow-up (Days 52-59) in the mITT population.

2.3.2. All-Cause Mortality (ACM) through the FU Visit

All-cause mortality through the FU Visit (Day 59) is defined as death due to any cause from the date and time of first dose of treatment through the FU Visit. Subjects who did not die or died after Day 59 or are lost to follow-up will be censored in the analysis at the last date known to be alive or Day 59, whichever is earlier.

2.3.3. Time to First Negative Blood Culture

Time to first negative blood culture is defined in hours from the first dose of study drug to the first negative blood culture without subsequent positive cultures following the first pre-treatment blood culture confirmed positive for any *Candida* species. Blood culture results from both location 1 and location 2 need to be negative if the samples were taken from 2 locations on the same day. Subjects will be censored at the earliest start date and time of receipt of a new antifungal (i.e., other than study drug) for the treatment of candidemia received any time on/after the date and time of the first dose of study drug if it was used prior to having a negative blood culture. If a subject is lost to follow-up or died prior to having a negative blood culture, the subject will be censored at the date of the last blood culture. The details about the censoring rules under different scenarios are shown in the following table:

Blood Culture Result	Antifungal Use	Event (Negative Culture) or Censor	Event or Censoring Date
Negative blood culture without subsequent positive cultures	Not used or used after negative blood culture	Event	Earliest blood culture date with negative result
Negative blood culture obtained prior to first dose date and no subsequent positive cultures	Not used or used after negative blood culture	Censor	First dose date
No negative blood culture	Not used	Censor	Last blood culture date
No negative blood culture	Used	Censor	Earlier date between the last blood culture date and the antifungal start date

The number and percentage of subjects with a negative blood culture at 24 and 48 hours post first dose will also be provided by treatment group. The denominator will include subjects who were either not censored in the time to negative blood culture analysis or who were censored after 24 or 48 hours, respectively.

